1 CHANGE OF CRO RESPONSIBLE FOR SAE/SUSAR REPORTING

Rationale

The CRO handling the SAE and SUSAR reporting have been replaced.

1.1 Amended Section

Section 8.2.5, Reporting of Serious Adverse Events

Changed from

An assigned contract research organisation (Drug Safety Navigator, DSN) will be responsible for reporting all SAEs to Regulatory Authorities (RA) in accordance with International Conference on Harmonisation, Good Clinical Practice (GCP) and local regulations.

As soon as the Investigator is aware of a potential SAE he/she should contact DSN by e-mail no later than 24 hours after the knowledge of such a case. At the time of initial reporting the investigator must provide as a minimum requirement, subject number, birth date, description of the SAE and a preliminary assessment of causality.

Contact Information:

CRO: **Drug Safety Navigator (DSN)**

e-mail: 

For fatal or life-threatening adverse events where important or relevant information is missing, active follow up is undertaken immediately. Investigators or other site personnel inform Hansa Biopharma and monitor of any follow up information on a previously reported SAE immediately but no later than within 24 hours of when he or she becomes aware of it. The monitor or Hansa Biopharma will advise the investigator/study site personnel how to proceed.

The SAE reporting procedures are detailed in the study specific Safety Management Plan. This plan is an agreement between the Hansa Biopharma, and DSN.

Changed to

An assigned contract research organisation (~~Drug Safety Navigator, DSN Primevigilance~~) will be responsible for reporting all SAEs to Regulatory Authorities (RA) in accordance with International Conference on Harmonisation, Good Clinical Practice (GCP) and local regulations.

As soon as the Investigator is aware of a potential SAE he/she should contact ~~DSN Primevigilance~~ by e-mail no later than 24 hours after the knowledge of such a case. At the time of initial reporting the investigator must provide as a minimum requirement, subject number, birth date, description of the SAE and a preliminary assessment of causality.

Contact Information:

CRO: **Drug Safety Navigator (DSN) Primevigilance**

e-mail: 

For fatal or life-threatening adverse events where important or relevant information is missing, active follow up is undertaken immediately. Investigators or other site personnel inform Hansa Biopharma and monitor of any follow up information on a previously reported SAE immediately but no later than within 24 hours of when he or she becomes aware of it. The monitor or Hansa Biopharma will advise the investigator/study site personnel how to proceed.

The SAE reporting procedures are detailed in the study specific Safety Management Plan. This plan is an agreement between the Hansa Biopharma, and ~~DSN Primevigilance~~.

1.2 Amended Section

Section 8.2.6, Reporting of Suspected Unexpected Serious Adverse Reactions (SUSARs)

Changed from

SUSARs with an outcome of death or which are life threatening must be reported to the relevant RAs within 7 calendar days, all other SUSARs must be submitted within 15 calendar days. The SUSAR reporting procedures are detailed in the study Safety Management Plan. This plan is an agreement between the Hansa Biopharma, and Drug Safety Navigator. Hansa Biopharma will notify the appropriate RA(s) and all participating study investigators of any SUSARs on an expedited basis and in accordance with applicable regulations. In addition, Hansa Biopharma is responsible for informing all investigators in all other ongoing studies involving imlifidase about all SUSARs.

Changed to

SUSARs with an outcome of death or which are life threatening must be reported to the relevant RAs within 7 calendar days, all other SUSARs must be submitted within 15 calendar days. The SUSAR reporting procedures are detailed in the study Safety Management Plan. This plan is an agreement between the Hansa Biopharma, and ~~Drug Safety Navigator~~ *Primavigilance*. Hansa Biopharma will notify the appropriate RA(s) and all participating study investigators of any SUSARs on an expedited basis and in accordance with applicable regulations. In addition, Hansa Biopharma is responsible for informing all investigators in all other ongoing studies involving imlifidase about all SUSARs.

1.3 Amended Section

Section 8.4, Pregnancy and Pregnancy Outcome

Changed from

If a subject becomes pregnant during the current study, the subject will continue in the study according to study protocol, if possible. A Pregnancy Report Form must be sent by the investigator to Drug Safety Navigator at the latest within two weeks of learning of the pregnancy. The outcome of all pregnancies (spontaneous miscarriage, elective termination, normal birth or congenital abnormality) will be followed up on the Pregnancy Report Form even after the subject has completed or discontinued the study. Drug Safety Navigator will follow up on pregnancy outcome 4 weeks after the projected due date.

Changed to

If a subject becomes pregnant during the current study, the subject will continue in the study according to study protocol, if possible. A Pregnancy Report Form must be sent by the investigator to ~~Drug Safety Navigator~~ *Primevigilance* at the latest within two weeks of learning of the pregnancy. The outcome of all pregnancies (spontaneous miscarriage, elective termination, normal birth or congenital abnormality) will be followed up on the Pregnancy Report Form even after the subject has completed or discontinued the study. ~~Drug Safety Navigator~~ *Primevigilance* will follow up on pregnancy outcome 4 weeks after the projected due date.

## List of abbreviations and definition of terms

ADA	Anti-drug antibody
ADaM	Analysis data model
AE	Adverse event
AMR	Antibody mediated rejection
CI	Confidence interval
CRF	Case report form
DSA	Donor specific antibodies, anti-human leukocyte antigen (HLA) donor-specific antibodies
EQ-5D-5L	EuroQol group 5 dimensions-5 levels
FAS	Full analysis set
KDQOL-SF 1.3	Kidney disease quality of live instrument – short form version 1.3
MedDRA	Medical Dictionary for Regulatory Activities
PT	Preferred term
QOL	Quality of live
SAB-HLA	Single antigen beads - human leukocyte antigen
SAE	Serious adverse event
SAP	Statistical analysis plan
SOC	System organ class
STDM	Study data tabulation model
TLF	Tables, listings and figures

## 1 Introduction

This document describes the planned processing and presentation of data and the statistical analyses for the study 17-HMedIdeS-14. This is a prospective long-term follow-up study including patients that have been treated with imlifidase in four previous studies – called the feeder studies. The feeder studies are: 13-HMedIdeS-02, 13-HMedIdeS-03, 14-HMedIdeS-04 and 15-HMedIdeS-06. There is no treatment with imlifidase in the current study.

The SAP is based on the protocol version 4.0 including amendment 03 dated 22 November 2021.

Because of the long-term follow-up nature of the study it is planned that yearly summary analyses of the data will be performed. A summary analysis can also be done ad hoc during the study.

### 1.1 Study objectives and endpoints

#### 1.1.1 Objectives

**The primary objective of this study is:**

The primary objective of this study is to evaluate graft survival in subjects who have undergone kidney transplantation after imlifidase administration.

**The secondary objectives of this study are:**

- Evaluation of long-term clinical outcomes of transplanted subjects treated with imlifidase in terms of patient survival, kidney function, comorbidity, treatments and quality of life.
- Assessment of safety blood sampling in transplanted subjects treated with imlifidase
- Assessment of donor specific antibodies (DSA) in transplanted subjects treated with imlifidase
- Assessment of immunogenicity (anti-drug antibodies, ADA) in transplanted subjects treated with imlifidase

#### 1.1.2 Endpoints

**The primary endpoint of this study is:**

The primary endpoint of this study is to determine overall graft survival, defined as time from transplantation to graft loss at 1, 2, 3 and 5 years after first dose of imlifidase. Graft loss is defined as: Permanent return to dialysis for at least 6 weeks, re-transplantation, or nephrectomy. If dialysis is used to define graft loss, the date of graft loss will be the first day of the last ongoing dialysis period reported (EMA Guideline on clinical investigation of immunosuppressants for solid organ transplantation 2008).

**The secondary endpoints of this study are:**

The following secondary endpoints will be evaluated after the first dose of imlifidase at the time points 1, 2, 3 and 5 years:

- Graft loss not censored for death (graft survival free of graft loss and death)
- Overall patient survival defined as time from transplantation to death for any cause

- Kidney function as evaluated by eGFR, P-creatinine, proteinuria
- Number of graft rejection episodes (classified by Banff, (Haas et al. 2018))
- Safety laboratory tests (haematology, total IgG)
- Treatment of graft rejection episodes
- Comorbidity
- DSA levels as evaluated by SAB-HLA analysis
- Presence of BK virus
- ADA as evaluated by anti-imlifidase IgG
- Health related quality of life (HR-QoL) as evaluated by patient questionnaires EQ-5D-5L and KDQOL-SF.

## 2 Study design

### 2.1 Overview of study procedures

Visit post imlifidase dosing	1 year 	2 years	3 years	5 years
Visit window	(+/- 2 months)	(+/- 4 months)	(+/- 4 months)	(+/- 6 months)
Informed consent	x 			
Eligibility	x 			
Enrollment and allocation of patient number	x 			
QoL questionnaires (EQ-5D-5L, KDQOL-SF)	x	x	x	x
Patient survival status	x 	x	x	x
Graft survival status	x 	x	x	x
Graft rejection episodes 	x	x	x	x
Kidney biopsy reports 	x	x	x	x
P-creatinine, eGFR calculation (performed by Sponsor)	x	x	x	x
Proteinuria (dipstick)	x	x	x	x
Hematology (Hemoglobin, Diff of leukocytes, Thrombocytes)	x	x	x	x
Total IgG	x	x	x	x
BK test	x	x	x	x
DSA (HLA antibody, Luminex) central lab	x	x	x	x
DSA (HLA antibody, Luminex) local lab	x	x	x	x
ADA (Anti-imlifidase IgG) central lab	x	x	x	x
Comorbidity 	x	x	x	x
Current immunosuppressive medication	x	x	x	x
Treatment of graft rejection episode (PE, IVIg, dialysis, other)	x	x	x	x
Adverse events 	x	x	x	x

. Some subjects will not perform all 4 visits because the study start will be after the subject's first visit should have taken place. If applicable, record creatinine and proteinuria results from planned time for 1- and 2 Years visits. End of Study (EOS) will occur 5 years (+/- 6M) after transplantation or earlier in the case of death, withdrawal of consent or lost to follow up.

. These activities shall be performed at subject's first visit that can take place 1, 2, or 3 years post imlifidase dose depending on when the subject was transplanted in the feeder study.

. After informed consent is obtained, pre-study visit data such as information on graft survival and patient survival can be collected and entered in the CRF. If applicable, record cause and date of death.

. Record biopsy proven graft rejection episodes (classified by the Banff classification) and creatinine and proteinuria results from the episode.

. If standard of care kidney biopsies are performed for any reason, at any time-point, e.g. suspected rejections, record information in the CRF.

. Record comorbidities that are medically relevant and registered in the subject's medical record. Medically relevant comorbidity are infections, malignancy, diabetes mellitus and cardiovascular events.

. Adverse events caused by a procedure in the protocol (blood sampling) or a clinically significant safety lab value are the only AEs that will be captured and reported. If the lab value is attributable to worsening renal function, graft rejection or natural progression of disease, it will not be reported as AE

### 2.2 Determination of sample size

As this is a non-interventional follow up study, no power calculation for sample size estimation was performed. All patients enrolled in the selected imlifidase kidney transplant studies will be considered for inclusion in this study. Up to 46 patients can be included, although the exact

number will depend on enrolment and patients' discontinuation figures in ongoing and/or selected clinical studies.

## 2.3 Blinding

This is an open study.

## 2.4 Data pre-processing

Data will be received from the data management database as SAS files in a raw data format and from the central laboratory in Excel files. Additionally, an excel file with acute rejection episodes during feeder studies will be provided by sponsor. All data will be converted to SDTM format using SDTM v1.4/SDTM IG v3.2 and will be documented by SDRG and define xml files. Further, SDTM data will be converted to ADaM data using ADaM 1.0/ ADaM IG v1.0 from which the production of tables, listings and figures will take place.

A study day variable is needed in several presentations and analyses. This could be derived as number of days since first administration of imlifidase or as the number of days since transplantation. For each subject, these dates are typically at most several days apart and, as the time span of the study is 5 years, the distinction between these two definitions is not important. All derivations of study day will therefore take first administration of imlifidase as the start day.

As a follow-up study, data that were collected in the feeder studies will in general not be re-collected. Relevant data are therefore copied from the feeder studies to the current study and included in the SDTM and the ADaM data sets. This is particularly relevant for the demographic data. The following table presents an overview of data types that will be retrieved from feeder studies.

Data type	Variables	Comment
Age		For demography presentations age at baseline will be used. For calculation of eGFR age at collection date will be used.
Other demography	Sex, race, country, site	
Baseline characteristics	Height, weight, BMI	
Transplant characteristics	Cross-match (positive/negative), delayed graft function, living or deceased donor, cold ischaemia time, number of historical transplantations	
SAB-HLA at pre-dose and 6 months		
eGFR, creatinine, proteinuria at pre-dose and 6 months		
ADA		

## EQ-5L-5D

The EQ-5D-5L questionnaire will be assessed at each visit. The EQ-5D-5L index value will be calculated according to User Guide EQ-5D-5L v2.1 April 2015 and based on the index value set as downloaded from <https://euroqol.org/eq-5d-instruments/eq-5d-5l-about/valuation-standard-value-sets/crosswalk-index-value-calculator/> on 23JAN2019. The study will include data from patients in Sweden, France and the USA. The downloaded index value table covers amongst others USA, France and Denmark, while it does not cover Sweden. For the Swedish patients, index values for Denmark will be used. Therefore, with these index value tables, a general index value will be looked up for each patient and visit.

## KDQOL-SF 1.3

The KDQOL-SF 1.3 will be assessed at each visit. The KDQOL-SF 1.3 questionnaire is available from the RAND homepage including descriptions and sample programs for converting scores.

This questionnaire combines a kidney specific part and a part on general health aspects taken from the SF-36 questionnaire. The following steps are needed: a) non-valid responses should be set to missing, b) reversal and normalisation of all responses so scores go from 0 (negative) to 100 (positive), c) taking average of all non-missing values within each scale.

The data will be condensed in the scales below:

Kidney disease (n = number of items in each scale):

Burden of kidney disease (n=4), Quality of social interaction (n=3), Cognitive function (n=3), Symptoms/problems (n=12), Effects of kidney disease (n=8), Sexual function (n=2), Sleep (n=4), Social support (n=2), Work status (n=2), Dialysis staff encouragement (n=2).

SF-36 (n = number of items in each scale):

Physical functioning (n=10), Role limitations—physical (n=4), Pain (n=2), Emotional well-being (n=5), Role limitations—emotional (3), Social function (n=2), Energy/fatigue (n=5), General health (n=5).

Further, the SF-36 composite physical T-score and the SF-36 composite mental score will be derived. These scores are normalised compared to a US mean of 50 with a standard deviation of 10, the SAS code for this derivation is downloaded from the RAND homepage.

## 3 Analysis sets

### 3.1 Full analysis set

The Full Analysis Set will be defined as all patients enrolled. Because of the non-interventional nature of this study no other analysis set will be defined and all data presentations and analyses will be based on the FAS.

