5. STUDY PROCEDURES

5.1 Study Visits

For each subject the duration of the study will not exceed 5 years and 6 months post imlifidase dosing.

All subjects considered for the study must be informed about the study, verbally and in writing, and give their written consent before any study procedure is performed. After informed consent is obtained, pre-study visit data such as information on graft survival and patient survival can be collected and entered in the CRF.

Some subjects will not perform all 4 visits because the study start will be after the subjects' first visit should have taken place.

If a subject is not able to attend a planned visit at the site, the visit can be performed remotely. The blood sampling should be performed at the local laboratory (if possible) and QOL forms

sent to the subject. The following activities and assessments will be performed at **1 year** (+/- 2 months), **2 years** (+/- 4 months), **3 years** (+/- 4 months) and **5 years** (+/- 6 months) **post imlifidase dosing:**

- Check of inclusion and exclusion criteria will be performed at the first visit for each subject after 1, 2 or 3 years post imlifidase dosing.
- Subjects shall complete QoL questionnaires (EQ-5D-5Land KDQOL-SF)
- Evaluation of graft survival
- Record patient survival (if applicable, date and cause of death)
- Safety laboratory tests (see Table 3)
- P-creatinine, eGFR and U-proteinuria tests
- DSA samples
- ADA sample
- BK virus sample
- Record comorbidity such as infections, malignancy, diabetes mellitus and cardiovascular events
- Record graft rejection episodes (classified by Banff)
- If applicable, record information from standard of care kidney biopsy reports
- Record treatments of graft rejection episodes (PE, IVIg, dialysis, other)
- Record current immunosuppressive medication
- Record and report AEs caused by study procedure or a clinically significant safety lab value

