5.2 Flow Chart

Table 2. Study flow chart.

Visit post imlifidase dosing	1 year ¹	2 years	3 years	5 years
Visit window	(+/- 2 months)	(+/- 4 months)	(+/- 4 months)	(+/- 6 months)
Informed consent	x ²			
Eligibility	x ²			
Enrollment and allocation of patient number	x ²			
QoL questionnaires (EQ-5D-5L, KDQOL-SF)	x	x	x	x
Patient survival status	x ³	x	x	x
Graft survival status	x ³	x	x	x
Graft rejection episodes ⁴	x	x	x	x
Kidney biopsy reports ⁵	x	x	x	x
P-creatinine, eGFR calculation (performed by Sponsor)	x	x	x	x
Proteinuria (dipstick)	x	x	x	x
Hematology (Hemoglobin, Diff of leukocytes, Thrombocytes)	x	x	x	x
Total IgG	x	x	x	x
BK test	x	x	x	x
DSA (HLA antibody, Luminex) central lab	x	x	x	x
DSA (HLA antibody, Luminex) local lab	x	x	x	x
ADA (Anti-imlifidase IgG) central lab	x	x	x	x
Comorbidity ⁶	x	x	x	x
Current immunosuppressive medication	x	x	x	x
Treatment of graft rejection episode (PE, IVIg, dialysis, other)	x	x	x	x
Adverse events ⁷	x	x	x	x

¹. Some subjects will not perform all 4 visits because the study start will be after the subject's first visit should have taken place. If applicable, record creatinine and proteinuria results from planned time for 1- and 2 Years visits. End of Study (EOS) will occur 5 years (+/- 6M) after transplantation or earlier in the case of death, withdrawal of consent or lost to follow up.

². These activities shall be performed at subject's first visit that can take place 1, 2, or 3 years post imlifidase dose depending on when the subject was transplanted in the feeder study.

³. After informed consent is obtained, pre-study visit data such as information on graft survival and patient survival can be collected and entered in the CRF. If applicable, record cause and date of death.

⁴. Record biopsy proven graft rejection episodes (classified by the Banff classification) and creatinine and proteinuria results from the episode.

⁵. If standard of care kidney biopsies are performed for any reason, at any time-point, e.g. suspected rejections, record information in the CRF.

⁶. Record comorbidities that are medically relevant and registered in the subject's medical record. Medically relevant comorbidity are infections, malignancy, diabetes mellitus and cardiovascular events.

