### 4.4 Endpoints

#### 4.4.1 Primary endpoint

The primary endpoint, overall graft survival, is defined as time from transplantation to graft loss evaluated at 1, 2, 3 and 5 years after first dose of imlifidase. Graft loss is defined as: Permanent return to dialysis for at least 6 weeks, re-transplantation or nephrectomy. If dialysis is used to

define graft loss, the date of graft loss will be the first day of the last ongoing dialysis period reported. The graft loss is evaluated at 1, 2, 3, and 5 years after dosing, but the time will be recorded as duration in days.

The primary endpoint will be analysed by the Kaplan-Meier survival method for the combined group with all feeder studies. The overall graft survival will be tabulated and presented graphically as a KM plot with 95% confidence limits, indicating the risk set per year and marking the censored observations. The following events will be censored at the time of occurrence: withdrawal from the study without graft loss, death not caused by graft loss, evaluation time point (the yearly evaluations - only for the annual reports not in the final reporting of the study) and end of study without graft loss. The survival percentage with 95% CI will be estimated at 1, 2, 3 and 5 years, or, for the yearly summary analyses as far as data allows.

The reason for graft loss will be displayed in a listing.

The protocol stipulates that explorative modelling of the influence of covariates on the graft loss may be defined in the SAP. With a maximum sample size of 46 patients and an expected small proportion of patients with graft loss, estimation of covariate parameters may be highly variable in which case the explorative modelling will not be performed.

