#### **4.4.2 Secondary endpoints**

##### **Graft loss not censored for death**

This endpoint is defined as the primary endpoint except that death for any cause also counts as a graft loss and therefore this event will not be censored in this case. The endpoint will be analysed and presented as the primary endpoint.

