##### **Overall patient survival**

The overall patient survival is defined as time from transplantation to death for any cause. This endpoint will be analysed and presented as for the primary endpoint. The following events will be censored at the time of occurrence: withdrawal from the study while alive, evaluation time point (the yearly evaluations) and end of study while alive.

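### Patient survival and graft loss not censored for death run from transplantation but are estimated only in subjects alive to consent 1 to 3 years later, so deaths before consent cannot enter either curve

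*SAP*

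**What the plan says.** SAP section 3.1 and protocol section 11.1.1 define the population in the same way: "The Full Analysis Set will be defined as all patients enrolled". Both add that no other set will be used for any analysis.

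Enrolment depends on consent. Protocol section 5.1 requires that subjects "give their written consent before any study procedure is performed". Footnote 2 to the flow chart (protocol section 5.2) places consent, eligibility and enrolment at the "first visit that can take place 1, 2, or 3 years post imlifidase dose". The documents describe no route by which a deceased recipient could be enrolled. The note in protocol section 4.2.1 on incomplete feeder-study participation does not waive consent.

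Both endpoints start earlier. In SAP section 4.4.2, "The overall patient survival is defined as time from transplantation to death for any cause". The composite takes over the primary definition, with the change that "death for any cause also counts as a graft loss and therefore this event will not be censored in this case". Both are analysed like the primary endpoint (SAP section 4.4.1): Kaplan-Meier, with a plot "indicating the risk set per year and marking the censored observations", and "The survival percentage with 95% CI will be estimated at 1, 2, 3 and 5 years". Delayed entry is not mentioned.

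Data from before the first visit are foreseen, but only once consent is given: "pre-study visit data such as information on graft survival and patient survival can be collected and entered in the CRF". SAP section 2.4 copies other data from the feeder studies (demographics, transplant characteristics, some laboratory values, rejection episodes). Deaths and graft losses are not in that list.

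**The concern.** This is immortal time. From transplantation to consent no enrolled subject can die, because dying would have prevented enrolment. An ordinary Kaplan-Meier nevertheless counts all enrolled subjects as at risk over that period. What is estimated is survival among people who lived long enough to consent, presented on a time axis that starts at transplantation.

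The two endpoints are affected differently. For patient survival, every event before consent is lost. For the composite, a graft loss before consent still counts if the subject lived to enrol, so only recipients who died before consent are lost.

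The synopsis says the study should inform future prescribers and patients about long-term benefit. A one-year survival figure that is close to 100% whatever happened to the early deaths would not do that unless it is labelled for what it is.

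**Working it through.** **1. The figure of 46.** Table 1 of the protocol gives 1 transplanted subject in study 02, 10 in study 03, 17 in study 04 (taking its total N as all transplanted) and 18 in study 06: 1 + 10 + 17 + 18 = 46. This reproduces the stated maximum, so 46 counts recipients whether or not they were alive when this study opened.

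**2. Time that cannot contain a death.** The visit windows are 1 year ± 2 months, 2 years ± 4 and 3 years ± 4, so consent falls in months 10–14, 20–28 or 32–40. A subject entering at Year 1 can be seen to die in at most 2 of the first 12 months (2/12 = 17%). A later entrant cannot be seen to die in any of them.

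**3. Year-1 patient survival.** Suppose k recipients die in year 1 before consent, and no enrolled subject dies in months 10–12.

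| k | All 46 | FAS |
|---|---|---|
| 1 | 45/46 = 97.8% | 100% |
| 2 | 44/46 = 95.7% | 100% |
| 3 | 43/46 = 93.5% | 100% |

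**4. Later time points.** Let k be all deaths before consent and d the deaths after it, with every survivor enrolled and followed completely. Then all-46 survival = (46 − k − d)/46 and FAS survival = (46 − k − d)/(46 − k). With d = 2:

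| k | All 46 | FAS |
|---|---|---|
| 0 | 44/46 = 95.7% | 44/46 = 95.7% |
| 1 | 43/46 = 93.5% | 43/45 = 95.6% |
| 3 | 41/46 = 89.1% | 41/43 = 95.3% |
| 5 | 39/46 = 84.8% | 39/41 = 95.1% |

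From k = 0 to k = 5 the all-46 figure falls 10.9 points and the FAS figure 0.5.

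**5. With assumed death rates.** Take a constant yearly death probability q, S(t) = (1 − q)^t, and entry at exactly 1, 2 or 3 years with shares w. FAS 5-year survival is S(5) / Σ w_a S(a). For q = 4% and equal thirds: S(5) = 0.96^5 = 81.5%; the share alive at entry is (0.960 + 0.922 + 0.885)/3 = 0.922; the FAS figure is 0.815/0.922 = 88.4%. For q = 2% the figures are 90.4% true and 94.1% FAS; for q = 6%, 73.4% and 83.0%. At q = 4% the FAS figure is 84.9% if all enter at Year 1, and 89.5% with entry split 20/30/50%. Neither q nor the split is in the documents.

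**6. The composite.** Three living subjects lose the graft at month 8 and enrol; three others die with a working graft at month 9. All 46: 40/46 = 87.0%. FAS: 40/43 = 93.0%. The gap comes only from the deaths.

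**7. When the direction reverses.** If m event-free survivors decline, FAS survival = (46 − k − d − m)/(46 − k − m), which equals the all-46 figure at m = 46 − k − 46d/(k + d).
- k = 1, d = 2: m = 14.3, so 15 of 43 must decline (28/30 = 93.3% against 93.5%).
- k = 3, d = 2: m = 24.6, so 25 of 41 (16/18 = 88.9% against 89.1%).
- k = 1, d = 4: m = 8.2, so 9 of 41 (32/36 = 88.9% against 89.1%).

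**8. What delayed entry can do.** At q = 4% with equal thirds, a large simulated sample analysed with delayed entry gave 85.2% at 5 years, against a true S(5)/S(1) of 0.96^4 = 84.9%. It recovers survival conditional on being alive at first entry, not the unconditional one-year figure. It does not suit the composite: with no deaths, three graft losses at month 8 and all 46 enrolling at month 12, the planned curve gives 43/46 = 93.5%, while delayed entry drops the three losses and gives 100%.

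**The case against.** The best defence is that this is a voluntary, descriptive follow-up study. Inclusion depends on willingness, so an analysis set of consented subjects is normal; both endpoints are secondary and nothing is tested. All of that is true, and it limits the weight of the point. It does not make a curve among survivors to consent into a curve from transplantation.

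Second, the plan does account for missing recipients. SAP section 4.2 covers all 46 in the disposition. Section 9.2 lists all transplanted patients (Listing 16.2.1.1) and patients excluded from the efficacy analysis (Listing 16.2.3.1), which may well identify those who did not enrol. These outputs do not feed the curves. A reader might also infer that the reports will carry no caveat. The documents do not support that: SAP sections 8 and 9 keep the output shells in separate documents, so footnotes and population labels are unknown.

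Third, the size is not anchored. Table 1 reports one graft loss in study 04 and one in study 06, and mentions no death. It is a brief summary of feeder studies followed for 6 months (2 months for study 02), with reporting of study 04 and the conduct of study 06 still ongoing, so silence is not evidence of no deaths. But every k above is an assumption, and k = 5 has no support in the text.

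**Conclusion.** The mechanism holds on the text. Followed as written, the plan cannot count a death before consent in either curve, treats that period as time at risk, and gives one-year patient survival of about 100% by construction. The one exception is a death in months 10–12 in a subject who enrolled early in the window.

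Three stronger readings are not supported.
- That the reported survival is in fact overstated: pre-consent deaths are unknown, and with none the bias is zero.
- That the bias must be upward: it is upward if survivors enrol, but enough refusals by event-free survivors can shrink or reverse it (step 7).
- That the primary endpoint is biased in the same way: it censors deaths not caused by graft loss, graft losses in living subjects enter retrospectively, and no direction can be fixed.

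The illustrations run from no difference to several points at 5 years and rest on assumed death counts, rates and entry splits. That the time before consent is immortal is near certain; the effect on the results is not known. The point should be fixed, because two named endpoints would otherwise describe a different quantity from the one defined.

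**What to change.** Amend SAP sections 3.1, 4.2 and 4.4.2, and record and date the departure from protocol section 11.1.1 in SAP section 6.

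(a) Estimate patient survival with delayed entry at consent, and report it as survival conditional on being alive at first entry. Do not add feeder-study time from enrolled subjects alone; that would recreate the immortal time.

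(b) Keep the FAS curve for the composite, because delayed entry would drop graft losses that happened before consent.

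(c) Label all FAS curves for these two endpoints *conditional on survival to enrolment*. Beside them, report how many of the 46 did not enrol because of death, with dates where known. If the disposition shells already plan this count, only the cross-reference is needed.

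(d) Where permission allows, add vital and graft status of all 46 recipients to the feeder-data import in SAP section 2.4 and show a supplementary Kaplan-Meier in all 46. For subjects of unknown status, recompute best-case and worst-case bounds from the data. A fixed 1/46 = 2.2 points per subject is right only with complete follow-up.

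Cost: (c) is SAP text and a disposition row. (a) needs one start–stop data set and gives small early risk sets. (d) depends on permission that cannot be assumed, since study 04 was investigator-sponsored. The figures may look slightly less favourable. SAP version 2.0 (4 April 2023) is already later than the planned last visit in 2022, so the change must be openly dated as late.
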